1. AMENDMENTS FROM PREVIOUS VERSION(S)

None.

2. INTRODUCTION

Rivipansel is being developed as a pan-selectin antagonist for the treatment of vaso-occlusive crisis (VOC) in subjects with Sickle Cell Disease (SCD). Both children and adults are affected, and greater mortality is seen in those with more severe disease.

Although rivipansel is known to be primarily eliminated by the kidney (>90% of dose excreted in urine based on data from the Single Ascending Dose study GMI-1070-101), hepatic function can have an effect on the PK of drugs for which the excretion is primarily renal. This study is therefore being conducted to evaluate the effect of hepatic impairment on the PK, safety and tolerability of rivipansel. Results from this study will be used in conjunction with collective safety, efficacy, and PK/pharmacodynamic (PD) data from other rivipansel studies to provide recommendations on dosing for subjects with hepatic impairment.

A single 840 mg dose of IV rivipansel will be used in this study as it is the dose selected for maintenance dosing in the rivipansel Phase 3 program. IV doses of rivipansel as high as 4 g (as a single dose) have been well tolerated in healthy volunteers. In the Phase 2 study multiple doses, using a loading dose of 40 mg/kg followed by doses of 20 mg/kg given every 12 hours for up to 7 days were also well tolerated. Therefore, it is expected that potential increases in exposure due to hepatic impairment with a single dose of 840 mg should not pose a safety concern. Single-dose administration was chosen because time-independent PK of rivipansel have been demonstrated at the anticipated concentrations, and thus single-dose PK will be able to adequately predict multiple-dose PK.

2.1. Study Design

This study is a Phase 1 open-label, single-dose, single-treatment, non-randomized study of rivipansel in subjects with moderate hepatic impairment and healthy subjects with normal hepatic function. Since rivipansel is primarily eliminated renally, a reduced study design with two groups (control subjects and subjects with moderate hepatic impairment) was considered adequate to characterize the PK in subjects with hepatic impairment. The Child-Pugh Score will be utilized to assess entry criteria and to assign subjects to the appropriate hepatic-impairment group. Child-Pugh assessments will be performed within the 14 days prior to study medication administration and Day 0 (baseline). Subjects should satisfy the criteria for Child-Pugh classification as Moderate Hepatic Impairment (Class B Score 7-9) for both assessments in order to be enrolled into the study. The subjects' hepatic function will be ranked based on clinical signs and liver function test results (Table 1).

Table 1. Child-Pugh Classification

Assessment Parameters	Assigned Score for Observed Findings		
	1 point	2 points	3 points
Encephalopathy Grade^a	0	1 or 2	3 or 4
Ascites	Absent	Slight	Moderate
Serum bilirubin (mg/dL)	<2	2 to 3	>3
Serum albumin (g/dL)	>3.5	2.8 to 3.5	<2.8
Prothrombin time (seconds prolonged)	<4	4 to 6	>6
Classification of clinical severity:			
Mild (Class A): Total score 5-6 points			
Moderate (Class B): Total score 7-9 points			
Severe (Class C): Total score >9 points			

a. Grade 0: Normal consciousness, personality, neurological examination, electroencephalogram.

Grade 1: Restless, sleep disturbed, irritable/agitated, tremor, impaired handwriting, 5 cps (cycles per sec) waves.

Grade 2: Lethargic, time-disoriented, inappropriate, asterixis, ataxia, slow triphasic waves.

Grade 3: Somnolent, stuporous, place-disoriented, hyperactive reflexes, rigidity, slow waves.

Grade 4: Unrousable coma, no personality/behavior, decerebrate, slow 2-3 cps delta activity.

A total of approximately 16 subjects will be enrolled; 8 subjects with moderate hepatic impairment and 8 healthy subjects with normal hepatic function. Healthy subjects with normal hepatic function will be enrolled after all of the subjects with moderate hepatic impairment have completed the in-patient portion of the study and will be matched for age, weight, and gender to the mean demographics of subjects in the moderate hepatic impairment group. Healthy subjects with normal hepatic function will be enrolled to enable comparison of PK parameters between healthy subjects and subjects with moderate hepatic impairment.

Subjects who withdraw from the normal hepatic function or moderate hepatic impairment groups for non-safety related reasons and who are considered to be non-evaluable with respect to the primary PK objective will be replaced at the discretion of the investigator and sponsor such that the number of completed subjects in each group equals eight.

2.2. Study Objectives

Primary Objectives

- *To evaluate the effect of moderate hepatic impairment on the PK of rivilansel following a single 840 mg IV dose.*

- *To evaluate the safety and tolerability of a single 840 mg IV dose of rivipansel in subjects with moderate hepatic impairment and in healthy subjects with normal hepatic function.*

Secondary Objective

- *To evaluate the effect of moderate hepatic impairment on additional PK parameters for rivipansel following a single 840 mg IV dose.*

3. INTERIM ANALYSES, FINAL ANALYSES AND UNBLINDING

No interim analysis is planned. Final analysis will follow the official database release. As this will be an open-label study, there is no formal unblinding of the randomization code.

4. HYPOTHESES AND DECISION RULES

4.1. Statistical Hypotheses

No hypotheses are required.

4.2. Statistical Decision Rules

No decision rules are required.

5. ANALYSIS SETS

5.1. Pharmacokinetic (PK) Analysis Set

5.1.1. Concentration Analysis Set

The PK concentration population is defined as all subjects treated who have at least 1 concentration.

5.1.2. Parameter Analysis Set

The PK parameter analysis population is defined as all subjects treated who have at least 1 of the PK parameters of primary interest.

5.2. Pharmacodynamic Analysis Set

None.

5.3. Safety Analysis Set

All subjects who receive at least 1 dose of study medication will be included in the safety analyses and listings.

5.4. Other Analysis Sets

None.

5.5. Treatment Misallocations

All analyses will be performed on an “as-treated” basis and will not include data from subjects who are randomized but not treated.

5.6. Protocol Deviations

Subjects who experience events that may affect their PK profile (eg lack of compliance with dosing) may be excluded from the PK analysis. At the discretion of the pharmacokineticist a concentration value may also be excluded if the deviation in sampling time is of sufficient concern or if the concentration is anomalous for any other reason.

A full list of protocol deviations will be compiled and reviewed to identify major and minor deviations prior to database closure.

5.6.1. Deviations Assessed Prior to Randomization

At Screening, the investigator will assess subjects against the inclusion and exclusion criteria as set out in Sections 4.1 and 4.2 of the protocol.

5.6.2. Deviations Assessed Post-Randomization

A full list of protocol deviations for the study report will be compiled prior to database closure. Any significant deviation from the protocol will be reviewed prior to database closure and a decision taken regarding evaluation for each analysis population.

6. ENDPOINTS AND COVARIATES

6.1. Efficacy Endpoint(s)

None.

6.2. Safety Endpoints

Any events occurring or increasing in severity following start of treatment will be counted as treatment emergent.

Events that occur in the Follow-up period will be counted as treatment emergent and causality attributed to the treatment taken.

The following data are considered in standard safety summaries (see protocol for collection days and list of parameters):

- *Adverse events,*
- *Laboratory data,*
- *Vital signs data,*
- *ECG results.*

Page 8 of 14

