## 4.1.3. Subjects with Hepatic Impairment

- 1. Satisfy the criteria for Child-Pugh classification as Moderate Hepatic Impairment (Class B Score 7-9) within the 14 days prior to administration of study medication and Day 0 (baseline) [Note: As stated in the STUDY DESIGN section, reasonable efforts will be made to enroll an adequate number of subjects (1 to 3 subjects) with Child-Pugh scores of 8 and 9 (based on assessment at Day 0) to ensure that the entire range of moderate hepatic impairment is represented].
- 2. Hepatic impairment due to primary liver disease and not secondary to other diseases, confirmed and documented by medical history, physical examination, liver biopsy, hepatic ultrasound, computed tomography (CT) scan or magnetic resonance imaging (MRI).
- 3. Stable hepatic impairment, defined as no clinically-significant change in disease status within at least the last 30 days, (no worsening clinical signs of hepatic impairment, or no worsening of total bilirubin or prothrombin time by more than 50%) as documented by the subject's recent medical history. If subjects do not have adequate available records, 2 screening visits (Screening and Day 0 visit) will be performed to demonstrate stability of hepatic disease. The 2 visits (if performed) for demonstrating stability of hepatic disease must be at least 7 days apart.
- 4. On stable doses of medication and/or treatment regimens for at least 4 weeks prior to screening. Such medications would also need to be held stable from screening through study completion. Subjects who are receiving a fluctuating treatment regimen may be considered for inclusion on a case-by-case basis if the underlying disease is under control in the opinion of the investigator and sponsor.

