## 5.6. Concomitant Treatment(s)

Healthy subjects with normal hepatic function will abstain from all concomitant treatments, except for the treatment of AEs, as described in the Healthy Subjects with Normal Hepatic Function section of this protocol. Use of prescription drugs, vitamins, or dietary supplements within 7 days or 5 half-lives (whichever is longer) prior to administration of study medication is not allowed. As an exception, acetaminophen may be used at doses of  $\leq 1$  g/day. Limited use of nonprescription medications that are not believed to affect subject safety or the overall results of the study may be permitted on a case-by-case basis following approval by the sponsor.

For subjects with impaired hepatic function, treatments intended for other indications should be administered as usual (Subjects with Hepatic Impairment).

All concomitant treatments taken during the study must be recorded with indication, daily dose, and start and stop dates of administration.

Treatments taken within 28 days before the dose of investigational product will be documented as prior treatments. Treatments taken after the dose of investigational product will be documented as concomitant treatments.

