#### 6.3. Follow-up Contact

• Each subject will have a follow-up phone call no earlier than 28 days and no later than 31 days after study medication administration to assess for AEs and SAEs.

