# 8.1.4. Time Period for Collecting AE/SAE Information

The time period for actively eliciting and collecting AEs and SAEs ("active collection period") for each subject begins from the time the subject provides informed consent, which is obtained before the subject's participation in the study (ie, before undergoing any study-related procedure and/or receiving investigational product), through and including a minimum of 28 calendar days after the last administration of the investigational product.

For subjects who are screen failures, the active collection period ends when screen failure status is determined.

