## 8.1.5. Causality Assessment

The investigator's assessment of causality must be provided for all AEs (serious and non-serious); the investigator must record the causal relationship on the CRF, and report such an assessment in accordance with the SAE reporting requirements, if applicable. An investigator's causality assessment is the determination of whether there exists a reasonable possibility that the investigational product caused or contributed to an AE; generally the facts (evidence) or arguments to suggest a causal relationship should be provided. If the investigator does not know whether or not the investigational product caused the event, then the event will be handled as "related to investigational product" for reporting purposes, as defined by the sponsor. If the investigator's causality assessment is "unknown but not related" to investigational product, this should be clearly documented on study records.

In addition, if the investigator determines that an SAE is associated with study procedures, the investigator must record this causal relationship in the source documents and CRF, and report such an assessment in the dedicated section of the CT SAE Report Form and in accordance with the SAE reporting requirements.

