# 8.2. Definitions

# 8.2.1. Adverse Events

An AE is any untoward medical occurrence in a study subject administered a product or medical device; the event need not necessarily have a causal relationship with the treatment or usage. Examples of AEs include, but are not limited to:

- Abnormal test findings;
- Clinically significant signs and symptoms;
- Changes in physical examination findings;
- Hypersensitivity;
- Progression/worsening of underlying disease;
- Drug abuse;
- Drug dependency.

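### SAP 6.2, read literally, makes every follow-up adverse event drug-related, against the investigator judgement in protocol 8.1.5; separately, no concomitant-treatment check is scheduled after Day 5.

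*SAP*

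**What the plan says.** **Causality.** SAP 6.2 first defines treatment-emergent events as those that start or worsen after treatment begins. It then adds: "Events that occur in the Follow-up period will be counted as treatment emergent and causality attributed to the treatment taken". The investigator is not mentioned. SAP 8.3.4 says only that adverse events are reported by hepatic function group under sponsor standards, which the documents do not reproduce.

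Protocol 8.1.5 says: "The investigator's assessment of causality must be provided for all AEs (serious and non-serious"), with the judgement recorded on the CRF. It has one default: "If the investigator does not know whether or not the investigational product caused the event, then the event will be handled as" related for reporting purposes. Protocol 8.2.1 lists "Progression/worsening of underlying disease" among its examples of adverse events.

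**Collection window.** Under protocol 8.1.4, events are actively collected from consent "through and including a minimum of 28 calendar days after the last administration of the investigational product". The last contact is a telephone call, "no earlier than 28 days and no later than 31 days after study medication administration to assess for AEs and SAEs" (protocol 6.3).

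**Concomitant treatments.** Protocol 5.6 says: "All concomitant treatments taken during the study must be recorded with indication, daily dose, and start and stop dates of administration". It counts any treatment taken after the dose as concomitant and sets no end date. Of impaired subjects' medicines, criterion 4 in protocol 4.1.3 says: "Such medications would also need to be held stable from screening through study completion". In the Schedule of Activities, the concomitant-treatment row runs from Day 1 to Day 5 and is blank for the call. Section 6.2.6 (Day 5) is the last visit list to include monitoring, and 6.3 names only AEs and SAEs.

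**The concern.** The two documents give different rules for the same variable. One takes causality from a clinical judgement on each event. The other, as worded, fixes it by the period in which the event occurs. Someone programming the related-event counts from SAP 6.2 could set every follow-up event to related, whatever the CRF says.

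The design makes this matter. Safety and tolerability in impaired subjects is a primary objective (protocol 2). All subjects receive rivipansel, and the comparison group is healthy. It therefore cannot show how often liver disease would worsen over a month without the drug, and the investigator's judgement is the main means of separating disease from drug.

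The concomitant-treatment gap is a separate matter, although it concerns the same weeks. A treatment started or changed after discharge is useful when a late event is judged. The protocol requires it to be recorded but schedules no contact at which anyone asks about it.

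**Working it through.** The plan states no figure on this point, so there is none to reproduce. The check compares the texts and sizes what depends on them.

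**1. The causality rules side by side**

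| | Protocol 8.1.5 | SAP 6.2, literal reading |
|---|---|---|
| Who decides | Investigator, for each event | Fixed by rule |
| When an event counts as related | When so judged, or when the investigator does not know | Whenever it occurs in follow-up |
| Late event judged unrelated | Unrelated | Related |

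The last row is the conflict. The opening of protocol 9 lets the SAP modify the protocol's analysis outline, but the SAP gives no reason for changing this rule and does not say which one governs the tables.

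**2. Treatment-emergent status.** An event that starts in follow-up has also started after treatment began, so it already meets the first sentence of SAP 6.2. Counting it also fits the 28-day collection period. Only the causality clause is at fault.

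**3. How much of the window is affected.** Inputs: discharge at 96 h, or 4 days after dosing (Schedule of Activities), and the call at 28 to 31 days (protocol 6.3). SAP 6.2 does not define the start of follow-up; I take it as discharge.

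- Call at day 28: (28 − 4)/28 = 24/28 = 85.7%
- Call at day 31: (31 − 4)/31 = 27/31 = 87.1%

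The same 24 to 27 days have no scheduled concomitant-treatment check.

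**4. Drug remaining at discharge.** Input: mean half-life of 6.67 to 7.41 h in healthy volunteers (protocol 1.2). Assuming decline at that half-life throughout, the fraction left is 0.5^(96/half-life).

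- 6.67 h: 96/6.67 = 14.4 half-lives, about 0.005% left
- 7.41 h: 96/7.41 = 13.0 half-lives, about 0.013% left
- Half-life doubled to 14.82 h (my assumption, since impaired subjects may differ): about 1.1% left

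On these figures follow-up falls almost wholly after the drug has gone. That makes an automatic attribution hard to justify, although it does not rule out a delayed effect.

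**5. What one event does.** With 8 subjects per group (protocol 9.1), one affected subject is 1/8 = 12.5 percentage points.

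**6. Illustration.** The documents give no background rate of disease-related events. If each impaired subject has an assumed probability p of at least one in follow-up, independently, the chance that at least one of the 8 is affected is 1 − (1 − p)^8:

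| Assumed p | Chance of at least one of 8 | Expected subjects |
|---|---|---|
| 5% | 34% | 0.4 |
| 10% | 57% | 0.8 |
| 20% | 83% | 1.6 |
| 30% | 94% | 2.4 |

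Under the literal rule, each such subject would be counted as having a drug-related event.

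**The case against.** The best defence is that the clause says which treatment a late event belongs to, not whether that treatment caused it. That is plausible. Other wording in this SAP does not fit the design: sections 3, 5.5, 5.6.1 and 5.6.2 refer to randomization in a non-randomized study, and 7.3 gives vomiting before absorption as an example for an intravenous drug. Nothing in SAP 6.2 cancels the CRF assessment, so the data for a correct table will exist. This makes an intended override doubtful. It does not rescue the clause, which is redundant on the benign reading and wrong on the literal one.

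A reader might infer four stronger points. The documents do not support them.

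- *That concomitant treatments are not collected after Day 5.* Protocol 5.6 requires them to be recorded, with no cut-off. What is missing is a scheduled check.
- *That information on concomitant medication is required only for serious events.* Protocol 8.1 calls for adequate information on each event. The sentence on concomitant medications follows text about requests from the sponsor's safety group, so its scope is arguable, but no such limit is written.
- *That follow-up events escape the new-or-worsened test.* They are a subset of events that already meet it.
- *That the impaired group will show an excess from disease alone.* No event rate is given. Protocol 4.1.3 requires hepatic disease to have been stable for at least 30 days, 4.2.3 excludes many other illnesses, and the SAP rule applies to both groups.

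**Conclusion.** The point stands as two corrections, each modest and cheap.

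First, SAP 6.2 and protocol 8.1.5 conflict on the literal reading. The result would be a wrong count of related events, in steps of 12.5 percentage points per affected subject within a group. Whether any event is misclassified depends on how the clause is programmed and on events that have not yet occurred. The probabilities above rest on assumed rates and measure opportunity, not expected bias.

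Second, the protocol is inconsistent with itself on concomitant treatments: 24 of 28 or 27 of 31 post-dose days have no scheduled check, against 5.6 and 4.1.3. This assumes that the study, for those two sections, runs to the follow-up call, which is the last scheduled contact. Neither section says so expressly.

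Neither point affects the pharmacokinetic analysis, and counting follow-up events as treatment emergent should stay.

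**What to change.** 1. **SAP 6.2.** Delete the causality clause, or replace it with a statement that causality is the investigator's assessment recorded on the CRF under protocol 8.1.5. Keep follow-up events as treatment emergent. This costs one line and should be done before database release.
2. **Protocol Schedule of Activities and 6.3.** Reconcile these with 5.6 and 4.1.3 by adding concomitant treatments to the 28 to 31 day call. This costs one more question on a call already planned, with its CRF entry and the protocol change; no extra visit is needed.

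Optional: show all-causality and investigator-assessed related events separately, or split the adverse event table at 96 h. The split would help a reader, but nothing in the documents requires it.

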6.3. Other Endpoints

6.3.1. PK Endpoints

Blood samples for PK analysis of PF-06460031 will be collected according to the Schedule of Activities given in the protocol.

The following PK parameters will be calculated for PF-06460031 (if possible) from the concentration-time data using standard non-compartmental methods:

Table 2. Noncompartmental PK Parameters

PK Parameter	Analysis Scale	PF-06460031
AUC _{inf} [*]	ln	A, D
AUC _{last}	ln	A, D
C _{max}	ln	A, D
T _{max}	R	D
t _{1/2} [*]	R	D
CL [*]	ln	D
V _{ss} [*]	ln	D

Key: A=analyzed using statistical model, D=displayed with descriptive statistics,
ln=natural-log transformed, R=raw (untransformed), *=if data permits

6.3.2. PD Endpoints

None.

6.4. Covariates

None.

7. HANDLING OF MISSING VALUES

For the analysis of safety endpoints, the sponsor data standard rules for imputation will be applied.

7.1. Concentrations below the Limit of Quantification

In all data presentations (except listings), concentrations below the limit of quantification (BLQ) will be set to zero. (In listings BLQ values will be reported as “<LLQ”, where LLQ will be replaced with the value for the lower limit of quantification).

7.2. Deviations, Missing Concentrations and Anomalous Values

In summary tables and plots of median profiles, statistics will be calculated having set concentrations to missing if 1 of the following cases is true:

1. A concentration has been recorded as ND (ie not done) or NS (ie no sample),
2. A deviation in sampling time is of sufficient concern or a concentration has been flagged anomalous by the pharmacokineticist.

Note that summary statistics will not be presented at a particular time point if more than 50% of the data are missing.

